#### **6.14.4. Vital Signs and Other Physical Findings**

As described more fully in compound level safety standards and in the laboratory-related PhUSE white papers (PhUSE 2013; PhUSE 2015), vital signs will be summarized similarly to the clinical laboratory evaluation (Table KGAD 6.12). For vital signs, treatment emergent low and high are based on a combination of a specified value and a change or percentage change for adults and adolescents as defined in the compound level safety standards.

**Table KGAD 6.12. Analysis Related to Vital Signs**

Analysis	Population
Box plots for observed values by visit	Modified Safety; Safety (sensitivity analysis)
Box plots for change from baseline values by visit	Modified Safety; Safety (sensitivity analysis)
Scatterplots of baseline-by-maximum values and baseline-by-minimum values	Modified Safety; Safety (sensitivity analysis)
Tables with the number and percentage of subjects who shift from normal/high to low (that is, treatment-emergent low) and the number and percentage of subjects who shift from normal/low to high (that is, treatment-emergent high); the limits are defined in the compound level safety standards	Modified Safety; Safety (sensitivity analysis)

#### **6.14.5. Immunogenicity**

An individual sample is potentially examined multiple times in a hierarchical procedure to produce a sample anti-drug antibody (ADA) assay result and may yield a sample neutralizing ADA (NAb) assay result. Treatment-emergent ADA (TE-ADA) are defined as those with a titer

2-fold (1 dilution) greater than the minimum required dilution if no ADAs were detected at baseline (treatment-induced ADA) or those with a 4-fold (2 dilutions) increase in titer compared to baseline if ADAs were detected at baseline (treatment-boosted ADA). A patient is considered TE-ADA positive when at least 1 postbaseline ADA sample meets the definition of TE-ADA.

Compound level safety standards (described in PSAP) will be followed in the analyses of immunogenicity. Listings of immunogenicity assessments will be provided-along with the summary of specified TEAEs by TE-ADA status for the Safety Population. The summary of TE-ADA and NAb status will be produced for the Modified Safety Population, where the postbaseline period for reporting is the same as described for AEs in Section 6.14.2. Additional assessments of the relationship between immunogenicity and efficacy will be performed as part of the integrated analysis including other Phase 3 lebrizumab AD trials.

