## Revisions in SAP Version 4:

Section	Description of Change	Rationale
Section 6.1.1	
 
Added 2 analysis populations (mITT Population and Modified Safety Population).
 
Removed “Unless otherwise specified, efficacy and health outcomes analyses will be conducted on this population” from the ITT Population and added to the mITT Population.
 
Removed “Safety analyses will be conducted on this population” from the Safety Population and added to the Modified Safety Population.
 
Removed “ITT” and added “mITT” and “Modified Safety” to analysis population in Table KGAD.6.2 for treatment comparison.
 
	In a directed site audit triggered by statistically implausible data at one study site, it was determined that some or all of the study participants at the site did not meet the eligibility criterion of having moderate-to-severe atopic dermatitis, and associated data was unreliable.
Section 6.7	
 
Added patient disposition summaries for the mITT Population.
 
	See above.
Section 6.8	
 
Updated analysis population from ITT to mITT for a summary of 
 
demographics and baseline characteristics, and
 
medical histories.
 
 
 
	See above.
Section 6.9	
 
Added treatment compliance for the Modified Safety Population.
 
	See above.
Section 6.10	
 
Updated analysis population from ITT to mITT for a summary of 
 
prior medications, and
 
concomitant medications.
 
 
 
Clarified analyses of rescue medication for AD will be based on mITT.
 
Clarified a listing of patients who use rescue medication will be based on ITT.
 
	See above.
Section 6.11	
 
Updated analysis population from ITT to mITT for all efficacy and health outcome analyses.
 
	See above.
Section 6.11.1	
 
Updated analysis population from ITT to mITT for the primary analysis of the primary outcome (IGA of 0 or 1 with at least 2-point reduction from baseline at Week 16) and the additional EMA primary outcome (EASI-75 at Week 16).
 
	See above.

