Section 6.14	
 
Updated the Modified Safety Population as primary analysis population for safety evaluations (exposure, adverse events, clinical laboratory data, vital signs, immunogenicity, adverse events of special interest).
 
Updated safety evaluations based on the Safety Population as sensitivity analysis
 
Clarified listings of immunogenicity assessments will be based on the Safety
 
	See above.

Section	Description of Change	Rationale
	Population.	
Section 6.15	
 
Updated analysis population from ITT to mITT for efficacy subgroup analyses.
 
	See above.
Section 6.14.5	
 
Removed “The subgroup analysis of efficacy by TE-ADA status (positive, negative) is described in the Section 6.15.1.”
 
	
 
Assessment of relationship between immunogenicity and efficacy to be performed as part of the integrated analysis including other Phase 3 lebrikizumab AD trials.
 

Section 6.16	
 
Removed languages related to the per-protocol (PP) population.
 
Clarified a listing of IPDs will be provided for the ITT Population.
 
	
 
Per-protocol set analyses not planned.
 
Clarification.
 

Abbreviations: AD = atopic dermatitis; EASI-75 =  $\geq 75\%$  reduction from Baseline in Eczema Area and Severity Index score; EMA = European Medicines Agency; IGA = Investigator’s Global Assessment; ITT = intent-to-treat; mITT = modified intent-to-treat; TE-ADA = treatment-emergent antidrug antibody.

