**Table KGAD.6.1. Analysis Populations**

Population	Description
All Entered Patients	All patients who signed informed consent. Patient flow will be summarized.
ITT Population	All randomized patients, even if the patient does not take the assigned treatment, does not receive the correct treatment, or otherwise does not follow the protocol. Patients will be analyzed according to the treatment to which they were assigned.
Modified ITT (mITT) Population	ITT Population excluding all patients from PPD . Patients will be analyzed according to the treatment to which they were assigned. Unless otherwise specified, efficacy and health outcomes analyses will be conducted on this population.
Safety Population	All randomized patients who received at least 1 dose of study treatment.
Modified Safety Population	Safety Population excluding all patients from PPD . Unless otherwise specified, safety analyses will be conducted on this population.

Abbreviation: ITT = intent-to-treat.

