### 6.14. Safety Analyses

The planned analyses of safety data will be performed with an intent to maintain consistency with compound level standard safety analyses (PSAP). These standards are based on internal standards which were informed by Clinical Data Interchange Standards Consortium (CDISC) standards, regulatory guidance (for example, FDA Clinical Review Template), and cross-industry standardization efforts (for example, Pharmaceutical Users Software Exchange [PhUSE] white papers from the Standard Analyses and Code Sharing Working Group provided in the PhUSE Computational Science Deliverables Catalog).

Safety evaluations will be based on the Modified Safety Population (Treatment Period). A sensitivity analysis will also be conducted on the Safety Population (Treatment Period).

Analysis populations are fully defined in [Table KGAD.6.1](#) while [Table KGAD.6.2](#) describes the treatment groups and the comparisons for each analysis population.

For document writing purposes for safety, tests with two-sided p-values less than 0.05 will be referred to as having strong statistical evidence for a treatment difference, unless otherwise noted. However, p-values should not be over-interpreted for these safety analyses. Except for pre-specified hypotheses, they correspond to data-driven hypotheses and hence are only useful as a flagging mechanism.

Not all displays described in this section will necessarily be included in the CSRs. Any display described and not provided in the CSR would be available upon request. Not all displays will necessarily be created as a “static” display. Some may be incorporated into interactive display tools instead of or in addition to a static display. Any display created interactively will be included in the CSR if deemed relevant to the discussion.

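### SAP 6.14.5 names only the Safety Population for the table of adverse events by TE-ADA status, in conflict with SAP 6.14 and with the companion TE-ADA summary

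*SAP*

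**What the plan says.** SAP Table KGAD.6.1 defines the Safety Population as "All randomized patients who received at least 1 dose of study treatment". The Modified Safety Population is the same set without the patients of one redacted source, and its entry adds: "Unless otherwise specified, safety analyses will be conducted on this population". The Version 4 revision table gives the reason. An audit of one site concluded that some or all of its participants did not have moderate-to-severe disease, "and associated data was unreliable".

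SAP 6.14 sets the rule for safety: "Safety evaluations will be based on the Modified Safety Population (Treatment Period)", followed by "A sensitivity analysis will also be conducted on the Safety Population (Treatment Period)".

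SAP 6.14.5 then covers immunogenicity in two consecutive sentences. The first reads "Listings of immunogenicity assessments will be provided-along with the summary of specified TEAEs by TE-ADA status for the Safety Population". The second begins "The summary of TE-ADA and NAb status will be produced for the Modified Safety Population". The section also says that compound-level standards will be followed, and it defers the relation between immunogenicity and efficacy to an integrated analysis across the Phase 3 program.

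**The concern.** Version 4 separates summaries from listings. Summaries move to Modified Safety, with the Safety Population as a check, and listings may stay on a wider set so that every patient remains visible. In 6.14.5 a summary is grouped with the listings and takes their population. A programmer who follows the sentence literally would run the adverse-event table on the Safety Population alone.

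Two things are at stake. First, this is the only place in the SAP where adverse events are to be related to antibody status. Safety subgroup work is deferred to the integrated analysis (6.15.2). Protocol 9.7 allows for an assessment of antibody impact on safety, and Protocol 8.4.7 requires an immunogenicity sample after a hypersensitivity reaction, so the question matters in this trial. Second, two tables that a reader will compare directly would rest on different patients.

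**Working it through.** No alpha, power or sample-size figure enters, so the check is a comparison of texts.

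| Output | Population named | Where |
|---|---|---|
| Safety evaluations in general | Modified Safety; Safety as sensitivity | SAP 6.14 |
| Default for safety analyses | Modified Safety, unless otherwise specified | Table KGAD.6.1 |
| Adverse-event summaries | Modified Safety; Safety as sensitivity | Table KGAD.6.10 |
| Adverse-event listings | ITT or Safety | Table KGAD.6.10 |
| Laboratory and vital-sign summaries | Modified Safety; Safety as sensitivity | Tables KGAD.6.11 and 6.12 |
| Antibody listings | Safety | SAP 6.14.5 |
| Adverse events by TE-ADA status | Safety | SAP 6.14.5 |
| TE-ADA and neutralizing antibody status | Modified Safety | SAP 6.14.5 |

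1. The general rule in 6.14 calls for a Modified Safety version of the adverse-event table. Section 6.14.5 names a population for that table, and it is a different one.
2. Table KGAD.6.1 yields to a specific statement elsewhere. Under that clause the wording of 6.14.5 can be taken as an exception, which leaves no stated version without the excluded site. No reason for an exception is given.
3. Let P be the number of TE-ADA-positive patients and N the number of TE-ADA-negative patients, with subscripts S (Safety), M (Modified Safety) and X (dosed patients at the excluded site). Then P_S = P_M + P_X and N_S = N_M + N_X. The two tables agree only if P_X = 0 and N_X = 0, that is, only if no patient at that site can be classified for TE-ADA.
4. Effect on a percentage. Suppose P_S = n, x of these patients report a given event, and one of the n comes from the excluded site. Removing that patient changes x/n to (x − 1)/(n − 1) or to x/(n − 1). The change is 0 when x = 0 or x = n, and it is at most 1/n in absolute value.
5. The documents give neither n nor the site's size. As an illustration only, assume a TE-ADA incidence of 2% to 5% among the planned 150 lebrikizumab patients: 150 × 0.02 = 3 and 150 × 0.05 = 7.5, so n is about 3 to 8. The upper limit 1/n is then 33 points at n = 3 and 12.5 points at n = 8, and the lower limit is 0 in both cases. If the site contributed 3 to 13 lebrikizumab patients (also assumed), the chance that at least one is TE-ADA-positive runs from 1 − 0.98^3 = 6% to 1 − 0.95^13 = 49%.

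**The case against.** The strongest reply is that 6.14 is unqualified and 6.14.5 never excludes other populations. The sentence could name one output on top of the general rule, and its punctuation suggests an editing slip. On that view a Modified Safety version is still due, and the program-level safety plan, which 6.14.5 invokes and which is not available here, may say so. This stands in part: it cannot be asserted that no version without the site will be produced. But the text states none, and a table whose population depends on which of two sections the programmer follows needs the same correction.

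Several stronger readings are tempting, and the documents do not support them.

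- A reader might infer that the Version 4 log keeps only the listings on the Safety Population. The log says "Clarified listings of immunogenicity assessments will be based on the Safety" Population, without the word only. It also names immunogenicity among the evaluations moved to Modified Safety. It hints at intent but proves nothing about the current text.
- A reader might infer that every other safety summary has both versions. The TE-ADA status summary names Modified Safety alone. SAP 6.14.6.8 says Safety in its text, while Table KGAD.6.20 says Modified Safety with Safety as sensitivity.
- A reader might infer that the site's adverse-event reports were specifically judged unreliable. The log speaks of eligibility and of associated data in general, and the SAP still uses the site in its safety sensitivity tables.
- A reader might infer a definite shift of 13 to 33 points. That needs an assumed incidence, an assumed TE-ADA-positive patient at the site and a particular event pattern. Under the assumptions above, such a patient is less likely than not, and the shift can be zero.

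**Conclusion.** The inconsistency is real on the current text. SAP 6.14.5 conflicts with 6.14, and its two sentences put linked antibody summaries on different populations. Taken literally, the adverse-event table includes the excluded site, has no stated counterpart without it, and may not reconcile with the TE-ADA status summary. This rests on the wording alone and does not need the revision log.

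The numerical effect is not known and should not be quoted. The consequence is limited to one descriptive safety table. The primary and multiplicity-controlled analyses, the power and the type I error are untouched. It is still worth correcting, because a stated rule is contradicted and the correction loses no information.

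**What to change.** Replace the sentences in SAP 6.14.5 that assign populations with wording to this effect: the immunogenicity listings use the Safety Population; the summary of TE-ADA and neutralizing antibody status and the summary of specified adverse events by TE-ADA status are both produced on the Modified Safety Population, with the Safety Population as sensitivity analysis. Keep the existing definition of the postbaseline period. The text of 6.14.6.8 can be aligned with Table KGAD.6.20 in the same edit.

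The cost is one sentence and reruns of existing tables. The Safety Population version is kept, so nothing now planned is given up.

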#### **6.14.6. Special Safety Topics including Adverse Events of Special Interest**

This section includes areas of interest whether due to observed safety findings, potential findings based on drug class, or safety topics anticipated to be requested by a regulatory agency for any reason. In general, potential adverse events of special interest (AESI) relevant to these special safety topics will be identified by one or more Standardized MedDRA Query(ies) (SMQs), by a Lilly-defined MedDRA PT listing based upon the review of the most current version of MedDRA, or by treatment-emergent relevant laboratory changes, as described below. Additional special safety topics may be added as warranted.

Unless otherwise specified, the special safety topics will be summarized for the Modified Safety Population and the Safety Population during the Treatment Period as described in Section 6.14.

Full details of the search terms and rules for deriving special safety topics in each of the sections below are described in the compound level safety standards along with information about the types of summaries and listings to be provided. In the event that the listing of terms or analysis changes for a special safety topic, it will be documented in the compound level safety standards which will supersede this document; it will not warrant an amendment to the individual study SAP.

##### **6.14.6.1. Hepatic Safety**

Hepatic labs include alanine aminotransferase (ALT), aspartate transaminase (AST), total bilirubin (TBL), and serum alkaline phosphatase (ALP).

**Table KGAD.6.13. Summary Tables Related to Hepatic Safety**

Analysis	Population

ALT and AST: The number and percentage of subjects with a measurement greater than or equal to 3 times (3X), 5 times (5X), and 10 times (10X) the performing lab upper limit of normal (ULN) during the treatment period for all subjects with a postbaseline value and for subsets based on various levels of baseline value
 
TBL and ALP: The number and percentage of subjects with a measurement greater than or equal to 2 times (2X) the performing lab ULN during the treatment period will be summarized for all subjects with a postbaseline value and for subsets based on various levels of baseline value
	
Modified Safety; Safety (sensitivity analysis)

Plot of maximum postbaseline ALT vs maximum postbaseline total bilirubin
	
Modified Safety Population for All Periods: ever on lebri and never on lebri;  Safety Population for All Periods: ever on lebri and never on lebri (sensitivity analysis)

Abbreviations: ALP = serum alkaline phosphatase; ALT = alanine aminotransferase; AST = aspartate transaminase; lebri = lebrikizumab; TBL = total bilirubin.

#### 6.14.6.2. Eosinophilia and Eosinophil-Related Disorders

In addition to the standard laboratory analysis (Section 6.14.3), eosinophilia and eosinophil-related AE will be summarized. Details regarding eosinophil-related PTs are in Compound Level Safety Standard.

**Table KGAD.6.14. Summary Tables Related to Eosinophil and Eosinophil-Related AE**

Analysis	Population

Shift table summarizing the number and percentage of participants within each maximum baseline category versus each maximum postbaseline category by treatment
	
Modified Safety; Safety (sensitivity analysis)

Summary of eosinophil-related TEAE by PT
	
Modified Safety; Safety (sensitivity analysis)

Abbreviations: AE = adverse event; PT = Preferred Term; TEAE = treatment-emergent adverse event.

#### 6.14.6.3. Infections, Including Herpes Infections and Relevant Parasitic Infections

Infections will be defined using the PTs from the MedDRA Infections and Infestations SOC. The MedDRA terms used to identify infections considered to be opportunistic infections (OI) in patients with immune mediated inflammatory conditions treated with immunomodulatory drugs are based on Winthrop et al. (2015) and are listed in the compound level safety standards. The

list contains narrow (more specific) and broad (less specific) PTs with respect to these prospectively defined OIs. Definitions of herpes infections, parasitic infections, and skin infections are listed in the compound level safety standards.

**Table KGAD.6.15. Summary Tables/Listings Related to Infection Related AE**

Analysis	Population
Summary of treatment-emergent infections by maximum severity	Modified Safety; Safety (sensitivity analysis)
Summary of serious infections by PT	Modified Safety; Safety (sensitivity analysis)
Summary of infection AEs resulting in permanent study drug discontinuation	Modified Safety; Safety (sensitivity analysis)
Treatment-emergent opportunistic and potential opportunistic infections	Modified Safety; Safety (sensitivity analysis)
Treatment-emergent adverse events – herpes and parasitic infections	Modified Safety; Safety (sensitivity analysis)
Treatment-emergent adverse events – skin infections	Modified Safety; Safety (sensitivity analysis)
Treatment-emergent adverse events – infections characterization from follow-up form	Modified Safety; Safety (sensitivity analysis)
A listing of patients with potential OI, serious infection, herpes and parasitic infections	Safety

Abbreviations: AE = adverse event; OI = opportunistic infections; PT = Preferred Term.

#### **6.14.6.4. Conjunctivitis**

Conjunctivitis are events of special interest and will be identified using PTs nested within the categories of conjunctivitis and Keratitis as described in the Compound Level Safety Standards:

**Table KGAD.6.16. Summary Tables/Listings Related to Conjunctivitis**

Analysis	Population
Summary of TEAE of conjunctivitis within categories	Modified Safety; Safety (sensitivity analysis)
TEAEs – conjunctivitis and eye inflammation characterization from follow-up form	Modified Safety; Safety (sensitivity analysis)
A listing of patients with conjunctivitis	Safety

Abbreviations: TEAE = treatment-emergent adverse event.

#### 6.14.6.5. Hypersensitivity

Potential hypersensitivity reactions will be determined using the following SMQs: anaphylactic reaction, hypersensitivity, and angioedema. Potential hypersensitivity will be categorized as immediate (that is, occurring the same day as drug administration) and non-immediate (that is, occurring after the day of study drug administration but prior to subsequent drug administration). The planned summaries are provided in [Table KGAD.6.17](#).

**Table KGAD.6.17. Summary Tables/Listings Related to Hypersensitivity**

Analysis	Population
Treatment-emergent adverse events – potential immediate hypersensitivity reactions (events occurring on day of study drug administration)	Modified Safety; Safety (sensitivity analysis)
Treatment-emergent adverse events – potential non-immediate hypersensitivity reactions (events occurring after the day of study drug administration)	Modified Safety; Safety (sensitivity analysis)

#### 6.14.6.6. Injection Site Reactions (ISR)

Injection site reactions (ISRs) are AEs localized to the immediate site of the administration of a drug. The evaluation of study drug related ISRs will be through the unsolicited reporting of ISR TEAEs. Injection site reactions will be defined using the MedDRA High Level Term (HLT) of Injection Site Reaction, excluding certain PTs related to joints and Administration Site Reactions as described in the Compound Level Safety Standards.

**Table KGAD.6.18. Summary Tables Related to Injection Site Reactions**

Analysis	Population
Summary of TEAE of ISR overall, and by PT	Modified Safety; Safety (sensitivity analysis)

Abbreviations: ISR = injection site reaction; PT = Preferred Term; TEAE = treatment-emergent adverse event.

